3.0 Inclusion and Exclusion Criteria

3.1 How individuals will be screened for eligibility

The first part of the screening interview can be conducted by phone and internet. It includes questions based on inclusion/exclusion criteria. Participants who meet criteria for entry into the study will be randomly assigned to BWL or DRL. Participants who are ineligible or decline participation will be thanked for their time and informed that they have completed the study.

3.2 Criteria that define who will be included or excluded in final study sample

Eighty autologous and allogeneic HSCT survivors will be recruited at Northwestern University, Feinberg School of Medicine, Department of Medical Social Sciences from Northwestern Memorial Hospital (NMH) and Robert H. Lurie Comprehensive Cancer Center (RHLCCC).

In order to qualify for participation in the study, potential participants must meet the following eligibility inclusion criteria:

1. Have a history of autologous or allogeneic HSCT,
2. Be in at least partial remission and not on active treatment (maintenance chemotherapy is ok),
3. Have less than severe graft-versus-host-disease (GVHD)
4. 1 to 5 years post-HSCT,
5. Age 21 or older,
6. English language proficient
7. Able to provide informed consent
8. Endorse subjective cognitive impairment.

Potential participants will not be allowed to participate in the study if they meet any of the following exclusion criteria:

1. Being treated for, or been diagnosed with or suspected neurological, psychiatric (including bipolar disorder or mania), or medical condition that might impair cognitive functioning (other than those caused by the cancer or its treatment),
2. Visual, hearing, or physical impairment sufficient to interfere with cognitive testing or participation,
3. Have a history of whole brain irradiation or surgery,
4. Active diagnosis of autoimmune and/or inflammatory disorder or disorders that may influence immune processes,
5. Have a history of severe graft-versus-host-disease
6. History of systematic light exposure treatment,
7. Diagnosed sleep apnea or narcolepsy,
8. Use of photosensitizing medications (including antibiotics that render participants photosensitive),
9. Plan to travel across meridians during the study,
10. Work night, early morning, or swing shifts,

PROTOCOL TITLE: Treating cognitive impairments in cancer patients via systematic light exposure

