7.3 Data to be collected

Measures

- 1) **Background Information (Screening and Time 1):** Sociodemographic data regarding gender, age, ethnicity, religion, income, marital status, employment status as well as questions about inclusion/exclusion criteria will be gathered during the screening assessment and any changes in information will be gathered at subsequent assessments. Medical data will be gathered through medical chart review and interview including comorbid and excluded medical conditions, medical information related to transplant, current prescription sleep-related and non-sleep-related medications, history of treatment with light therapy, and remaining exclusion criteria. The Self-administered Comorbidity Questionnaire will be used to capture comorbid conditions and the Valdimarsdottir Infection Scale will be used to capture recent infections. Recent Changes in Care will be evaluated by asking questions about any changes in medical treatment in Times 2 and 3 assessment time points.
- 2) **Active Psychosis (Screening):** The 6-item Paranoia/Psychoticism Screener (PPS) based on the "Psychotic Symptoms" module of the Structured Clinical Interview for DSM-IV-TR Axis I Disorders (SCID)⁴⁵ that has good discriminant validity will be used to exclude participants with active psychosis.
- 3) **Suicidality (Screening):** Participants will be asked questions regarding suicidal ideation, including one item from the Brief Symptom Inventory (BSI),⁴⁶ "Over the last week, have you had thoughts of ending your life" that will be used to screen for active suicidal ideation. Additional questions will be asked to assess for active suicidality. Those who are actively suicidal will be referred for further assessment and treatment, and their physician and/or a psychosocial staff member will be contacted. The PI will also follow up with the participant.
- 4) **Substance Abuse (Screening):** Current substance abuse (not including tobacco use) will be assessed by combining the 4-item Rapid Alcohol Problems Screen (RAPS-4)⁴⁷ with the Two-Item Conjoint Screening (TICS)⁴⁸. Questions endorsed will be followed up with additional questions to determine alcohol or drug abuse/dependence. Both measures have good sensitivity and specificity.^{47, 48} Participants determined to have probable current substance abuse disorder will be ineligible for the study and referred for further assessment and treatment.

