- 7) **Subjective Cognitive Function (Times 1, 2, 3, and 4):** The Cognitive Failures Questionnaire is a 25-item self-report measure of cognitive difficulties in everyday life using a 5-point Likert scale. Its reliability and validity are well-documented. Those who score ≥ 43 are deemed to have clinically significant impairment. This measure has been used widely in the measurement of cognitive assessment, including for cancer-related cognitive impairment (e.g., Calvio, Peugeot, Bruns, Todd, & Beuerstein, 2010; Scherling, Collins, MacKenzie, Lepage, Bielajew, & Smith, 2012). Patient Assessment of Own Functioning Inventory – a 33-item self-report measure of a patient's self-perceptions regarding their functioning in everyday tasks and activities.
- 8) **Neurobehavioral functioning (Times 1, 2, 3, and 4):** The Frontal Systems Behavior Scale is a reliable and valid measure of neurobehavioral functioning (Grace & Malloy, 2001)
- 9) **Sleep Quality (Times 1, 2, 3 and 4):** The Pittsburgh Sleep Quality Index consists of 19 self-rated items (35). Scale reliability is excellent using both an internal consistency criterion (Cronbach's alpha = 0.83) and test-retest reliability ($r = 0.85$). The validity of the instrument is based on its ability to discriminate patients (those having either sleep problems and/or depressive symptoms) from controls (healthy participants without sleep complaints).
- 10) **Chronotype (Time 1):** The Morningness-Eveningness Questionnaire: A reduced scale (MEQr) will be used to collect data on baseline circadian predispositions (Horne & Ostberg, 1976; Adan & Almirall, 1991). It is a 5-item self-rated survey designed to measure whether a person's peak alertness is in the morning or evening. This measure takes approximately 1 minutes to complete.
- 11) **Physical health (Time 1):** Physical health measures will be included as covariates in data analyses as they have been shown to be associated with fatigue, sleep, depressed

PROTOCOL TITLE: Treating cognitive impairments in cancer patients via systematic light exposure

mood, and cognition.⁵⁷⁻⁶⁶ We will include Body Mass Index (a measure of adiposity) calculated by dividing a participant's weight by the square of their height. The World Health Organisation classifies a body mass index of 25-29.9 as overweight, 30-34.9 as obese class I, 35-39.9 as obese class II, and ≥ 40 as obese class III.

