17) Usage (during light exposure): To measure adherence and fidelity to the procedures, the integrated meter in the Litebooks® record time and duration the light box turned on each day. Participants will also record when they turn on and off the light box and reasons for non-participation in a Litebook Log.

18) Actigraphy (Times 1, 3, and 4): Sleep/wake activity and CAR will be recorded with the Actiwatch-2 (Mini Mitter /Phillips/Respirronics), which is similar in size to a watch and worn on the nondominant wrist. Total sleep time, percent sleep, total wake time, number of awakenings per night, length of awakenings at night, percent awake, and napping behavior (number of naps; naptime) will be computed. The actigraph also records light and amount (lux) and duration (above 1000 lux) of light exposure. Each participant will wear the actigraph for 7 consecutive days at each of the 3 time points and complete a sleep log on which they will record time to bed, time awake and other information to be used in

PROTOCOL TITLE: Treating cognitive impairments in cancer patients via systematic light exposure

editing and scoring the data. For CAR, the activity data will be fit to an extended cosine model¹⁰⁹ from which circadian variables will be computed: acrophase (time of maximum modeled activity), amplitude (difference between maximum and minimum activity), mesor (mean of the modeled activity curve), and pseudo F-statistic (measure of rhythm robustness). There was no evidence of phase advance in [name]'s data, but we will control for it statistically if it exists.

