9.0 Data and Specimen Management

9.1 Data analysis plan

Descriptive statistics will be calculated for the entire group and separately for each treatment group. T-tests and Fisher's exact tests will be used to assess group differences at baseline for possible confounders (i.e., demographic variables, and clinical characteristics *including time since transplant*). Variables showing differences between the two groups will be used as covariates in subsequent analyses. Since there is no known seasonality effect on cognitive functioning, seasonality will not be controlled in these analyses.

Aim 1: Assess the feasibility and acceptability of BWL as an intervention for CRCI in HSCT survivors. Feasibility: We will adhere to currently accepted practice for feasibility studies¹¹⁰ by measuring the number of eligible patients, willingness of participants to be randomized, follow-up rates, the number who cease the intervention and their specific concerns about the intervention. We will monitor adherence by examining integrated meter data (i.e., time and duration of light box use). We expect high adherence, but if there is variation in duration, we will use duration as a predictor of the outcomes. Participants will be asked to log light box use (beginning and ending time) and reasons for not using it if that occurs. There is no gold standard for what constitutes a “feasible” study and relevant CRCI intervention feasibility studies have not been home-based.^{18, 111} Nevertheless, in an inpatient cognitive rehabilitation study of HSCT patients, 78% completed baseline, intervention, and time 2 assessments.¹⁸ A light exposure feasibility study for seasonal affective disorder deemed a 68% completion rate as acceptable,¹¹² and this is the criteria we will use in this study. In [name]'s pilot study, breast cancer

PROTOCOL TITLE: Treating cognitive impairments in cancer patients via systematic light exposure

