- b) The results of Aim 2 will provide evidence that BWL reduces cognitive impairment. Mediation analyses using bootstrapping will provide estimates of the effect of light treatment on the mediators, the effect of the mediators on cognitive functioning, the direct effect of light treatment on cognitive functioning, and the indirect effect of light treatment on cognitive functioning whilst accounting for the mediators. Advantages of this method include: 1) it does not rely on the causal steps approach to mediation analysis;^{114, 115} 2) bootstrapping of the sampling distribution does not rely on the assumption of normal sampling distributions of the indirect effects; 3) type II error is reduced because it requires fewer inferential tests; and iv) multiple mediators can be tested at once;¹¹⁶ 4) allows for statistical control of covariates. For this exploratory analysis, we will examine each category of factors as mediators separately (i.e., sleep, chronobiological, biological, and psychological factors).

Missing data: We will be using a mixed linear model using a maximum likelihood approach to parameter estimates which means that not every participant has to provide full data.

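### Apart from physical health measures, covariates are chosen by baseline arm imbalance, which does not protect the non-randomised mediator-to-cognition path in the exploratory mediation analysis

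*Combined protocol and SAP*

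**What the plan says.** Section 9.1, Exploratory Aims b), will estimate four quantities by bootstrapping: the effect of light on the mediators, the effect of the mediators on cognition, and the direct and indirect effects of light on cognition. Sleep, chronobiological, biological and psychological mediators are examined as separate categories. On covariates, the section lists as an advantage that the method "allows for statistical control of covariates". It gives no list, no baseline mediator or baseline cognition term, no statement about unmeasured confounding and no sensitivity analysis.

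The general covariate rule opens section 9.1: "T-tests and Fisher's exact tests will be used to assess group differences at baseline for possible confounders". The candidates are "demographic variables, and clinical characteristics", including time since transplant. Then: "Variables showing differences between the two groups will be used as covariates in subsequent analyses". No significance threshold is given. The mediation analysis comes later in the same section, so the rule reaches it.

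Two places in section 7.3 depart from that rule. Item 11 says: "Physical health measures will be included as covariates in data analyses as they have been shown to be associated with fatigue, sleep, depressed" mood and cognition. That choice does not depend on arm balance; BMI is the only measure named. Item 18 says of a circadian phase advance, "but we will control for it statistically if it exists", which concerns a feature of the rhythm and not a baseline common cause.

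Other plausible common causes are collected but given no such role. Section 7.3 item 1 records age, comorbidity, transplant information and "current prescription sleep-related and non-sleep-related medications"; item 6 measures premorbid ability. The inclusion criteria in section 3.2 admit less than severe graft-versus-host disease (GVHD) and note that "maintenance chemotherapy is ok".

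**The concern.** Randomisation protects the light-to-mediator and light-to-cognition comparisons. It does not protect the mediator-to-cognition path, because nobody is randomised to a level of sleep quality, rhythm, cytokines or fatigue. On that path a confounder is any variable that affects both mediator and cognition, whether or not the arms differ on it. Age, comorbidity, maintenance therapy or sleep medication could each qualify with the arms perfectly balanced. A screen for arm differences asks the wrong question here. Under randomisation it will also usually leave such a variable out.

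At stake are Hypothesis 3, Exploratory Aim 1 and Exploratory Aim 2b. A marker that light shifts, but that has no effect on cognition, could be put forward as the mechanism.

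**Working it through.** The plan states no power or effect size for the mediation analysis, so there is no figure of its own to reproduce. The check asks how often a false indirect effect would appear.

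**Inputs**
- 40 per arm and alpha 0.05 (section 9.2; two-sided assumed).
- Light effect on the mediator a = 0.63 SD (section 9.2, sleep quality only).
- True mediator effect on cognition b = 0.
- One stable common cause C, independent of arm, correlating r within arm with both mediator M and cognition Y. The documents give no r, so 0.1 to 0.5 is shown.
- C enters the model only if its baseline t-test gives p < 0.05 (threshold assumed).

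**Model.** M = a·arm + r·C + √(1−r²)·e₁ and Y = r·C + √(1−r²)·e₂.

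**Step 1: how often the screen admits C.** C is randomised, so at a 0.05 threshold it is admitted in about 5% of trials (simulated 4-5%) and left out in about 95%.

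**Step 2: bias.** With C left out, the coefficient of Y on M given arm is r² instead of 0. The expected false indirect effect under the screen is 0.95 × 0.63 × r². At r = 0.5 this is 0.95 × 0.63 × 0.25 = 0.150 SD (simulated 0.15).

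**Step 3: false-positive rate by hand.** The interval excludes zero roughly when both paths are significant.
- Light-to-mediator: d = 0.63 with 40 per arm has power 0.79.
- Mediator-to-cognition: the standard error is √(1−r⁴)/√77. At r = 0.5 this is 0.968/8.775 = 0.110, so the ratio is 0.25/0.110 = 2.27 and the probability of significance is 0.61.
- Under the screen: 0.95 × 0.79 × 0.61 + 0.05 × 0.79 × 0.05 = 0.46.

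**Step 4: simulation.** Repeated simulations of this design gave the fifth column. One used percentile bootstrap intervals, as the plan intends, for r of 0.3 and above.

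| r | Bias in b (r²) | False indirect effect, SD | By hand | Simulated, plan's screen |
|---|---|---|---|---|
| 0.1 | 0.01 | 0.006 | 4% | about 4% |
| 0.2 | 0.04 | 0.024 | 5% | about 5% |
| 0.3 | 0.09 | 0.054 | 10% | about 10% |
| 0.4 | 0.16 | 0.096 | 22% | 20-24% |
| 0.5 | 0.25 | 0.150 | 46% | 44-49% |

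With C always in the model, the simulated rate is about 3-6% throughout and the mean indirect effect is 0.00. For a stable cause, adding only baseline mediator and baseline cognition gives roughly 4-8%.

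**Step 5: sensitivity**
- A looser screen helps little. At r = 0.5 the false effect is 0.90 × 0.63 × 0.25 = 0.142 at a 0.10 threshold and 0.80 × 0.63 × 0.25 = 0.126 at 0.20 (simulated 0.14 and 0.13).
- If light does not move the mediator (a = 0), the mediator-to-cognition coefficient is still biased (0.24 at r = 0.5). The mean indirect effect is then 0.00, and the interval excludes zero in 2% of trials.

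**The case against.** The strongest reply is that the mediation paragraph states no selection rule, so the fair complaint would be an unspecified covariate list. This stands in part: the imbalance rule reaches mediation only through its reference to later analyses. But it is the plan's only general rule and nothing exempts mediation from it. A reader might infer that every mediation covariate is chosen by imbalance. The documents do not support that, because item 11 of section 7.3 commits physical health measures on a sound criterion, association with the mediators and cognition.

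Second, the exclusions in section 3.2 remove several strong common causes: diagnosed sleep apnea and narcolepsy, shift work, inflammatory disorders, severe GVHD, and other conditions that impair cognition. This stands, and it makes large r less likely. Age, milder GVHD, maintenance therapy and medication remain.

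Third, the size rests on assumed correlations. That also stands. At r of 0.2 or below there is essentially no inflation, and 0.63 is the sleep quality figure, from a comparison that was not significant. The documents give no standardised effect for cytokines.

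A reader might also infer that changes in care during treatment create a larger error that must always be adjusted away. Figures for that case depend on a baseline-to-follow-up correlation the documents do not give, so none is claimed. Change in care arises after randomisation and light may affect it, so adjusting for it could remove part of a true indirect effect or bias the randomised light-to-mediator path.

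**Conclusion.** The point holds in this limited form. Outside physical health measures, the plan selects covariates by a criterion that does not address confounding of the mediator-to-cognition path, and no other provision fills the gap. A false mediation finding needs two conditions: light shifts the mediator, and a common cause correlates about 0.3 or more with both mediator and cognition. The false-positive rate then rises from near nominal to about 10% at 0.3 and 44-49% at 0.5. This rests on 40 per arm with complete data, a = 0.63, a single stable cause and an assumed screening threshold of 0.05.

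It would go too far to say that balanced common causes will be reported as mediation, or that the larger trial will pursue the wrong mechanism. The plan labels this analysis exploratory and ties the larger trial to preliminary efficacy. Exploratory Aim 2a is a randomised comparison and, like the main BWL-DRL comparisons, is unaffected. The change is worth making because mediation by rhythm and sleep is a stated hypothesis and the remedy uses data already collected.

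**What to change.** In section 9.1, Exploratory Aims b):

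1. State that covariates in the mediation models are not chosen by differences between arms.
2. Always include the Time 1 value of the mediator and of cognition, plus a short fixed set of baseline variables already collected. For example: age, premorbid ability, BMI, comorbidity score, transplant type, baseline maintenance or GVHD therapy, and baseline sleep medication.
3. State the assumption of no unmeasured mediator-outcome confounding.
4. Add one sensitivity analysis showing how large a residual mediator-cognition correlation would have to be to remove the indirect effect.
5. Keep change in care out of the main model. Show it, at most, in a sensitivity model beside the main one.

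The cost is wording and degrees of freedom. The example set has 7 variables; with the 2 baseline terms that is 9, if each takes one degree of freedom. With intercept, arm and one mediator, 80 − 12 = 68 residual degrees of freedom remain with complete data. At the plan's 68% completion criterion, 0.68 × 80 is about 54 participants, leaving about 42, so the set should stay short, especially where a category enters several mediators together. No visit, measure or participant burden changes.

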9.2 Power analyses

Aim 1 Power: Based on [name]'s pilot study with 10 breast cancer patients, the effect size indicated that we would need a sample size of 19 to achieve power at 0.80. However, the sample size is likely too small to provide reliable estimates of improvement in cognitive functioning. One of the main aims is to determine preliminary efficacy of the intervention in preparation for a larger scale trial. For a total sample of 80, we calculated the mean difference between the two treatment arms for the Neurocognitive (composite) Index and assumed a repeated measures design with an autoregressive lag 1 error structure and autocorrelation of 0.60. The difference able to be detected with power equal to 0.80 and alpha = 0.05, is 0.209.

Aim 2 Power: Our preliminary R-21 study that examined BWL vs. DRL on cancer-related fatigue in a mixed cancer population (including HSCT) provided guidance for the power. Sleep Quality: While survivors in the BWL group had better sleep quality scores than the DRL group, the main effect for treatment was not statistically significant, no doubt due to sample size. Cohen's d was 0.63. For a repeated measures design with alpha equal to 0.05 and a sample size of 40 per group, power=0.99. CAR: There was significant time x treatment interaction (p=0.02) on the F statistic. We calculated power for a repeated measures design with autoregressive lag 1 structure and autocorrelation of 0.60. With alpha equal to 0.05 and sample size of 40 per group, power=0.99. Fatigue: As with CAR, there was significant time x treatment interaction (p=0.003). Using the same method as above, power = 0.99. Depressed mood: There was a significant (p=0.004) time x treatment interaction. Using the same method as above, power = 0.99.

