patients used the light box about 50% of the required days. This usage frequency was sufficient for cognitive improvement to occur in the BWL group. A 50% level of adherence will be considered acceptable in this study. Acceptability: As recommended in the literature, in addition to accrual rates, we will assess acceptability by evaluating participants' comments about the intervention after they have had experience with it.¹¹³ Finally, a comparison of the BWL and DRL on the FACIT-TS-G will be conducted using t-tests. Significant differences in favor of the BWL condition are expected.

Aim 2: Examine whether BWL compared with DRL among HSCT survivors suffering from cognitive impairment yields significant improvements in cognitive functioning. We will examine the cognitive functioning subscales and composite scores in separate analyses. Linear mixed model analysis with repeated measures will be conducted using the SAS procedure MIXED.

Contrasts will compare groups across assessments. The linear mixed model approach has a range of choices for the error variance/covariance structure and accommodates missing data thus protecting against a "completers only" bias. Since multiple outcomes will be correlated with one another, *p*-values for significance will be Sidak-adjusted for multiple comparisons. If there is variation in light box utilization, we will use duration time as a predictor of the outcome measures as in Aim 1. No pre-intervention bias favoring BWL over DRL is anticipated. However, we will test this assumption by crossing expectancy with the treatment condition. This interaction is not expected to be significant. These results will determine preliminary efficacy and sustainability of the intervention.

Power: Based on [name]'s pilot study with 10 breast cancer patients, the effect size indicated that we would need a sample size of 19 to achieve power at 0.80. However, the sample size is likely too small to provide reliable estimates of improvement in cognitive functioning. One of the main aims is to determine preliminary efficacy of the intervention in preparation for a larger scale trial. For a total sample of 80, we calculated the mean difference between the two treatment arms for the Neurocognitive (composite) Index and assumed a repeated measures design with an autoregressive lag 1 error structure and autocorrelation of 0.60. The difference able to be detected with power equal to 0.80 and alpha = 0.05, is 0.209.

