Aim 3: Examine whether BWL compared with DRL affects sleep and psychological variables (depressed mood, fatigue) which have been implicated as correlates of cognitive functioning in cancer patients. Hypothesis 2: Sleep quality and psychological variables will improve in the BWL group compared to the DRL group. The Aim 1 analytic strategy will be used in the analysis of this aim. Power: Our preliminary R-21 study that examined BWL vs. DRL on cancer-related fatigue in a mixed cancer population (including HSCT) provided guidance for the power. Sleep Quality: While survivors in the BWL group had better sleep quality scores than the DRL group, the main effect for treatment was not statistically significant, no doubt due to sample size. Cohen's *d* was 0.63. For a repeated measures design with alpha equal to 0.05 and a sample size of 40 per group, power=0.99. CAR: There was significant time x treatment interaction (*p*=0.02) on the F statistic. We calculated power for a repeated measures design with autoregressive lag 1 structure and autocorrelation of 0.60. With alpha equal to 0.05 and sample size of 40 per group, power=0.99. Fatigue: As with CAR, there was significant time x treatment interaction (*p*=0.003). Using the same method as above, power = 0.99. Depressed mood: There was a significant (*p*=0.004) time x treatment interaction. Using the same method as above, power = 0.99.

Exploratory Aims: Explore a) whether BWL compared with DRL affects biological (inflammatory immune response) variables; and b) whether the effects of BWL compared to

PROTOCOL TITLE: Treating cognitive impairments in cancer patients via systematic light exposure

DRL on cognitive functioning are mediated by sleep, chronobiological factors (i.e., circadian activity rhythms), biological factors (i.e., inflammatory immune response), and psychological factors (i.e., fatigue, depressed mood).

- a) Assess whether the BWL intervention affects biological factors (IL-1ra, IL-6, IL-8, IL-10, sTNF-III, CRP, PBMCs, and intracellular RNA) that have been identified as correlates of CRCI. Biological variables will be measured at Times 1 and 2. The mixed linear model approach described in Aim 2 will be used here.

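### Is the 0.99 power quoted for sleep quality overstated?

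*Combined protocol and SAP*

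**What the plan says.** Section 9.2 takes its sleep-quality effect from the preliminary study of light and cancer-related fatigue. There, it says, "the main effect for treatment was not statistically significant, no doubt due to sample size". It then gives the standardised effect and the claim: "Cohen's d was 0.63. For a repeated measures design with alpha equal to 0.05 and a sample size of 40 per group, power=0.99". The same text stands in section 9.1 under Aim 3.

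The next sentences concern circadian rhythm: "We calculated power for a repeated measures design with autoregressive lag 1 structure and autocorrelation of 0.60". Fatigue and depressed mood are then said to use that same method. Sleep quality comes before the sentence and is not tied to it. The other place where an autocorrelation of 0.60 appears is the power statement for the cognitive composite.

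On the analysis, Aim 3 in 9.1 says: "The Aim 1 analytic strategy will be used in the analysis of this aim". In 9.1, Aim 1 is feasibility and acceptability, with descriptive summaries and a t-test on treatment satisfaction. The repeated-measures mixed model is under Aim 2, where the contrast is described only as "Contrasts will compare groups across assessments".

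Section 7.3, item 9, schedules the sleep index at all four time points and quotes a test-retest correlation of 0.85 for it. Section 6.1 lists it as a secondary endpoint.

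**The concern.** Of the four 0.99 figures, this is the only one given with an effect size, so it is the one a reader will try to check. The natural attempt is a two-sided comparison of arm means over the post-baseline visits, with the AR(1) 0.60 that appears nearby. That gives 0.92, a type II error of about 8% where the plan implies 1%. On that reading, reaching 0.99 would take about 64 per group, or about 50 with baseline adjustment, instead of 40.

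The pointer to the Aim 1 strategy adds to the doubt. Read literally, it sends the sleep outcome to a feasibility analysis and leaves the tested contrast undefined. If the figure were wrong, the plan would be promising more for this endpoint than it can deliver.

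**Working it through.** **Inputs from the documents.** d = 0.63, 40 per group, alpha 0.05, stated power 0.99 (9.2); four measurements, the first before treatment (7.1.1, 7.3); AR(1) 0.60, stated for other outcomes (9.1, 9.2); sleep-index retest correlation 0.85 (7.3).

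**Assumptions.** Two-sided test, d standardised by the single-visit SD, full effect at Times 2 to 4, no dropout.

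**Formula.** If the analysed contrast has variance v relative to a single visit, the noncentrality is 0.63 × √(40/2) / √v = 2.817/√v, referred to a noncentral t with 78 df (77 if baseline-adjusted). Power of 0.99 needs v of about 0.432.

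**Stated figure.** A single measurement (v = 1) gives 0.795, so 0.99 depends on the repeated measures. How much they add depends on inputs that are not given.

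**AR(1) 0.60, equally spaced visits.**
- Mean of three post-baseline visits: v = [3 + 2(0.60 + 0.60 + 0.36)]/9 = 0.680; power 0.921.
- Mean of all four visits: v = [4 + 2(3 × 0.60 + 2 × 0.36 + 0.216)]/16 = 0.592; power 0.951. This puts the full effect at Time 1, before treatment.
- Baseline-adjusted: the covariance of baseline with the post-baseline mean is (0.60 + 0.36 + 0.216)/3 = 0.392, so v = 0.680 − 0.392² = 0.526; power 0.970.
- Baseline-adjusted with efficient (GLS) weights: v = 0.485; power 0.979.
- Change from baseline: v = 0.680 + 1 − 2 × 0.392 = 0.896; power 0.836.

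None of these is 0.99.

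**Other ordinary inputs, still two-sided and 40 per group.**

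| Correlation | Contrast | v | Power |
|---|---|---|---|
| Compound symmetry 0.50 | baseline-adjusted | 0.667 − 0.50² = 0.417 | 0.991 |
| Compound symmetry 0.60 | baseline-adjusted | 0.733 − 0.60² = 0.373 | 0.995 |
| AR(1) 0.85 | change from baseline | 0.872 + 1 − 2 × 0.729 = 0.414 | 0.991 |
| AR(1) 0.85 | baseline-adjusted | 0.872 − 0.729² = 0.340 | 0.998 |
| AR(1) 0.85 | unadjusted post-baseline mean | 0.872 | 0.846 |
| AR(1) 0.36 | mean of all four visits | 0.423 | 0.990 |

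**Actual visit times.** The visits are not equally spaced. Measured from the start of treatment they fall at roughly weeks −1, 2, 4 and 12. If a correlation of 0.60 is taken to apply per 2, 3 or 4 weeks and decays with elapsed time, the baseline-adjusted mean gives 0.986, 0.986 and 0.989. GLS weighting gives 0.988, 0.989 and 0.992. The unadjusted post-baseline mean gives 0.973, 0.952 and 0.933.

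**The cross-reference.** Section 9.2 labels the cognitive power statement Aim 1 and the sleep, rhythm, fatigue and mood statement Aim 2. Section 9.1 prints the same two texts under Aims 2 and 3. The numbering has moved by one. The Aim 1 strategy named under Aim 3 is therefore evidently the strategy for cognition, the mixed model.

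**The case for a change.** The strongest case for a change is that the text names a treatment main effect and the plan does not list the baseline value as a covariate. Only variables found to differ between arms at baseline are to be adjusted for. The plainest contrast is therefore unadjusted, and at AR(1) 0.60 it gives 0.92 to 0.95. At 0.85 it falls further, to 0.85. The readings that reach 0.99 need inputs the text does not state, and stating them would take one sentence. The figure also allows for no dropout: with 27 per group (68% of 40, the feasibility criterion) analysed as complete cases at AR(1) 0.60, power runs from 0.79 (unadjusted) to 0.90 (GLS, baseline-adjusted).

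Much of this stands. The inputs are not written down, and the unadjusted two-sided main effect does not reach 0.99 at 0.60. What does not stand is the step to an overstatement. The 0.60 is borrowed from other outcomes. The equal-spacing convention behind 0.97 is a common choice but does not match the schedule. Replacing 0.99 with 0.92 to 0.97 would exchange one figure with unstated inputs for another whose inputs come from the reader. The dropout illustration is a worst case, since the planned mixed model also uses partial data, and it concerns an endpoint the trial was not sized for.

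**Conclusion.** The 0.99 cannot be verified from the text, but it is not shown to be wrong. Under the assumptions above, power is 0.92 to 0.95 unadjusted and 0.97 to 0.98 baseline-adjusted at equally spaced AR(1) 0.60. It is 0.99 or more under several other ordinary choices. If d was already scaled to the analysed contrast, power is 0.795. The unstated contrast and correlation decide which of these applies.

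Nothing in the trial turns on the answer. Sleep quality is secondary, the total of 80 is not derived from it, and the main readings from 0.92 to 0.99 clear 0.80 comfortably. No test, estimate or conclusion would differ. The Aim 1 pointer is a numbering slip that an analyst would resolve to the mixed model from 9.1 and 9.2 together. What remains is missing detail behind one secondary power figure and a clerical cross-reference. Neither calls for a change to the plan.
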